2. Change from Day 1 and shifts from Day 1 in all safety laboratory parameters;
3. Change from Day 1 in vital signs and significant changes in physical examination abnormalities.

Number of Subjects/Sample Size Assumptions:

The study will enroll approximately 390 subjects. The proportion of subjects in the placebo control group achieving a HiSCR at Week 12 is estimated to be approximately 30%. The attrition rate throughout the trial is estimated to be approximately 7%. A sample size of approximately 130 subjects per treatment group (390 in total) at a Type I error rate of two-sided $\alpha = 0.05$ provides approximately 90% power to detect a 20% superiority of avacopan compared to the placebo control group in HiSCR at Week 12, assuming an HiSCR at Week 12 of 50% in the avacopan group.

Study Interventions/Methodology

Eligible adult subjects (at least 18 years of age) with moderate to severe hidradenitis suppurativa (Hurley Stage II or III) as specified by the eligibility criteria are allowed to enter the study.

In Period 1, subjects will be randomized 1:1:1 to receive 10 mg avacopan twice daily, 30 mg avacopan twice daily or matching placebo for 12 weeks in a double-blind, placebo-controlled manner.

To obtain balance across treatment groups, a stratified randomization scheme will be implemented. The stratification factors and strata within each factor are listed below. Eligible subjects will be randomized with equal chance (i.e., 1:1:1) to one of the three treatment groups within each stratum based on a non-dynamic, list-based blocked randomization scheme.

1. Hurley Stage (Stage II vs. III):
 - a. Stage II disease: one or more widely separated recurrent abscesses with tract formation and scars, or
 - b. Stage III disease: multiple interconnected tracts and abscesses across an entire area, with diffuse or near diffuse involvement.
2. Concomitant antibiotic therapy (Yes vs. No)
 - a. Concomitantly treated with doxycycline or minocycline as the only allowed antibiotic treatment for HS, or
 - b. No concomitant antibiotic therapy.
3. Anti-TNF- α treatment (Treatment naïve vs. Previous treatment):
 - a. Did not previously receive anti-TNF- α drug such as adalimumab or infliximab (anti-TNF- α drug naïve), or
 - b. Previously (but no longer) received an anti-TNF- α drug and
 - completed anti-TNF- α treatment but may have relapsed, or
 - was intolerant to anti-TNF- α treatment, or

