8.8.5. Safety Analyses

All subjects who are randomized and received at least one dose of study drug will be included in the safety population.

All clinical safety and tolerability data will be summarized by treatment group and listed by treatment group and by subject.

All reported adverse events will be coded using MedDRA and listed by System Organ Class, Preferred Term, and verbatim term.

- Treatment-emergent adverse events will be summarized and listed by treatment group by System Organ Class and Preferred Term, by relatedness and by maximum severity.
- Treatment-emergent serious adverse events and adverse events leading to withdrawal will be summarized by treatment group.

Individual vital signs and change from baseline in vital signs will be summarized by treatment group and listed by treatment group, subject, and study visit.

Laboratory data will be listed by treatment group, subject, and study visit. Abnormal laboratory values will be flagged. Laboratory data (actual values and change from baseline) will be summarized by treatment group and study visit. Shift tables will be generated for shifts in laboratory parameters by study visit.

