- 14. Proportion of subjects who start disallowed opioid pain therapy during Period 1 and Period 2 including the follow-up period separately;
- 15. Proportion of subjects who undergo lesion intervention due to HS during Period 1 and Period 2 including the follow-up period separately;
- 16. Number of lesion interventions due to HS during Period 1 and Period 2 including the follow-up period separately;
- 17. Health-economic information:
 - a. WPAI:SHP: Change from Baseline to each timepoint during Period 1 and Change from Week 12 to each timepoint during Period 2 and including the follow-up period;
 - Hospitalizations (cumulative): Number of Hospitalizations total and due to HS, Number of days hospitalized, Number of days missed from work during Period 1 and Period 2 including the follow-up period separately;
 - c. Emergency or Urgent Care visits (cumulative): Number of visits total and due to HS, Number of days (or hours where applicable) missed from work during Period 1 and Period 2 including the follow-up period separately;
 - d. Lesion interventions for HS: Number of days (or hours where applicable) missed from work due to HS lesion interventions during Period 1 and Period 2 including the follow-up period separately.

B. Safety Endpoints

- Subject incidence of treatment-emergent serious adverse events, adverse events, and withdrawals due to adverse events;
- Change from Baseline and shifts from Baseline in all safety laboratory parameters;
- Change from Baseline in vital signs and significant changes in physical examination abnormalities.

IV. Study Design

A. Design Overview

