The AE listings will be prepared, sorted chronologically within subjects for the following types of AEs. Each listing will include system organ class, preferred term, onset and end date, severity, relation to study drug, action taken, outcome, and SAE status.

- All AEs
- Serious AEs
- TEAEs leading to death
- TEAEs leading to withdrawal the study drug
- TEAEs of special interest

B. Clinical Laboratory Results

Laboratory test results include:

- Hematology: hemoglobin, hematocrit, RBC count, WBC count with differential, platelet count, mean cell hemoglobin, mean cell hemoglobin concentration, mean corpuscular volume.
- Serum Chemistry: liver panel (total bilirubin, lactate dehydrogenase, aspartate
 aminotransferase [AST], alanine aminotransferase [ALT]), renal panel (blood
 urea nitrogen, creatinine), creatine phosphokinase (CPK), albumin, sodium,
 potassium, magnesium, bicarbonate, chloride, calcium, inorganic phosphorus,
 glucose, total protein, alkaline phosphatase, total cholesterol, uric acid, serum
 amylase, and serum lipase.
- Urinalysis: nitrite, blood, and protein. If positive, microscopy will be performed;
- Virology (measured only at screening and may be measured at the local laboratory): hepatitis B surface antigen, hepatitis C antibodies, HIV 1 and 2 antibodies.
- TB screen: interferon γ release assay (IGRA).
- Pregnancy test: serum pregnancy test

All laboratory values will be converted to International System of Units (SI units). Lab results will be graded by the low/normal/high classifications based on normal ranges.

Laboratory data (actual values and change from baseline) will be summarized with the mean, standard deviation and median by treatment group and study visit. Laboratory data will be listed by treatment group, subject, and study visit. The CTCAE grades will be provided for selected Lab parameters. Abnormal laboratory values will be flagged.

The subject incidence of elevated laboratory values of ALT, AST, total bilirubin, alkaline phosphatase as assessed by the Central Laboratory, will be summarized by treatment group and Grade, as defined per Common Terminology Criteria for Adverse Events (CTCAE) Version 5. Shift from baseline to highest CTCAE grade during the study period will also be produced for these laboratory parameters based on the Central Laboratory measurements.

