The same summary by treatment and CTCAE grade will be produced for subject incidence of elevated creatine phosphokinase (CPK), low neutrophils, low lymphocytes, low leukocytes, low hemoglobin, and low platelets. Shift from baseline to highest CTCAE grade during the study period will also be produced for these laboratory parameters. A by-subject listing including all data for these laboratory parameters including CTCAE grade for subjects with any abnormality will be provided

Urine and serum pregnancy test results for female only, HIV screening results, Hepatitis B/C screening results, and tuberculosis screening results will be listed.

C. Vital Signs

The following vital signs variables will be summarized: systolic blood pressure (mmHg), diastolic blood pressure (mmHg), temperature (°C) and heart rate (beats/min) and weight (kg). The following summaries will be provided:

- A summary of the absolute and change from Baseline value for each vital sign variable by treatment group, visit, and period.
- A summary of the number and percentage of subjects experiencing at least one Potentially Clinically Significant Vital Sign Findings by treatment group and visit.

Definitions of Potentially Clinically Significant Vital Sign Findings

Parameter (unit)	Category	Markedly Abnormal Values
Systolic	Low	≤ 90 mmHg or decrease ≥ 20 mmHg from
Blood	Value	Baseline
Pressure	High	≥180 mmHg or increase ≥ 20 mmHg from
(mmHg)	Value	Baseline
Diastolic	Low	≤ 50 mmHg or decrease ≥ 15 mmHg from
Blood	Value	Baseline
Pressure	High	≥105 mmHg or increase ≥ 15 mmHg from
(mmHg)	Value	Baseline
Heart Rate	Low	≤ 50 bpm or decrease ≥ 15 bpm from
(bpm)	Value	Baseline
1	High	≥ 120 bpm or increase ≥ 15 bpm from
	Value	Baseline

A by-subject listing of all vital signs data will be provided. This listing will be presented by treatment group with abnormal vital sign values flagged as "L" or "H" accordingly.

D. 12-Lead Electrocardiogram (ECG)

ECG results will be listed in the data listings. Abnormal ECG findings will be listed by treatment group and study visit, and clinical significance of abnormalities indicated.

E. Physical Examination

Physical examination will include assessment of appearance/mental status, head, eyes, ears, nose, throat, and the following body systems: dermatologic, cardiovascular, respiratory, gastrointestinal, musculoskeletal and neurologic.

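### The safety endpoint covers shifts in all laboratory parameters, but SAP IX.B specifies shift tables for only ten of them, and not by visit

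*Protocol*

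**What the plan says.** **Endpoint.** The protocol lists "Change from Day 1 and shifts from Day 1 in all safety laboratory parameters" as a safety endpoint in the synopsis and again in Section 8.6. SAP III.B carries it over as "Change from Baseline and shifts from Baseline in all safety laboratory parameters". Laboratory change is also part of the primary safety objective (protocol 2.1, SAP II.A).

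**Protocol analysis.** Section 8.8.5 states: "Shift tables will be generated for shifts in laboratory parameters by study visit". It names no subset of parameters.

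**SAP analysis (IX.B).** Two groups of parameters get CTCAE incidence summaries:
- "The subject incidence of elevated laboratory values of ALT, AST, total bilirubin, alkaline phosphatase as assessed by the Central Laboratory";
- "elevated creatine phosphokinase (CPK), low neutrophils, low lymphocytes, low leukocytes, low hemoglobin, and low platelets".

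For each group the SAP adds: "Shift from baseline to highest CTCAE grade during the study period will also be produced for these laboratory parameters". For laboratory data in general it says: "Laboratory data (actual values and change from baseline) will be summarized with the mean, standard deviation and median by treatment group and study visit". It also plans listings with abnormal values flagged, and a low/normal/high classification of results against normal ranges. No table is tied to that classification.

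**Precedence and declared changes.** SAP I.A says that its definitions and methods override those of the protocol. SAP Section X records the CTCAE analyses as an addition. It says nothing about narrowing the set of parameters or replacing by-visit shifts.

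**The concern.** A stated safety endpoint and the analysis meant to deliver it do not match. The mismatch lies inside the SAP (III.B against IX.B) as well as between SAP and protocol. A programmer building tables from IX.B would produce worst-grade shifts for ten parameters and nothing categorical from the laboratory data for the rest.

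Shift tables count the individuals who move out of range. Means and medians by visit are poor at that, because a few large changes barely move them. Without a shift or incidence table, no planned laboratory table would say how many subjects in each arm developed, for example, a high creatinine, lipase or potassium.

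**Working it through.** No figure in the plan needs reproducing. The check is a count, followed by an illustration with assumed values.

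**1. Parameters with a specified shift table (SAP IX.B).**
- Elevated liver tests: ALT, AST, total bilirubin, alkaline phosphatase = 4.
- CPK (high); neutrophils, lymphocytes, leukocytes, hemoglobin, platelets (low) = 6.
- Total 4 + 6 = 10. Each is graded in one direction, to the highest grade over the study period.

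**2. Parameters listed in SAP IX.B.**

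| Group | Listed | With shift table | Without |
|---|---|---|---|
| Serum chemistry | 22 | 5 | 17 |
| Hematology excluding differential | 8 | 3 | 5 |
| WBC differential | 2 to 5 (assumed) | 2 | 0 to 3 |
| Urinalysis | 3 | 0 | 3 |
| **Total** | **35 to 38** | **10** | **25 to 28** |

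The documents do not list the differential cells, so the range runs from the two named in the shift tables to an assumed five-part differential. The share without a shift table is 25/35 = 71% to 28/38 = 74%.

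The 17 chemistry analytes are LDH, BUN, creatinine, albumin, sodium, potassium, magnesium, bicarbonate, chloride, calcium, inorganic phosphorus, glucose, total protein, total cholesterol, uric acid, amylase and lipase.

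**3. Timing.** Protocol 8.8.5 plans shifts by study visit. IX.B plans one shift per subject, to the worst grade. So even the ten covered parameters do not get the table that the protocol describes.

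**4. What the continuous summary would show.** Assume 130 subjects in an arm, three of whom have a creatinine rise of 160 umol/L at the same visit, with mean change 0 in the others.
- Shift in the mean: 3 × 160/130 = 3.7 umol/L. The median is essentially unchanged.
- SD of change, if the others do not vary: √(3 × 160²/130 − 3.69²) = √(590.8 − 13.6) ≈ 24.
- SD of change, if the others have an SD of 10: √(577.1 + 100 × 127/130) ≈ 26, against 10 without the three.
- If the three rises fall at three different visits, each visit has one: mean shift 160/130 = 1.2, SD √(160²/130 − 1.23² + 100 × 129/130) ≈ 17.

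If these rises took the subjects from normal to high, a worst-value shift table would show three subjects in either case. The inflated SD signals that something happened, but not to how many subjects or in which direction.

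**The case against.** The strongest reply is that these abnormalities are not hidden. Protocol 7.2.3 counts abnormal laboratory findings among possible adverse events, and SAP IX.A tabulates treatment-emergent events by system organ class and preferred term. Protocol 7.2.3.6 has the investigator review abnormal reports and the Medical Monitor review notable ones. The SD is planned, and SAP VI.L (with protocol 8.8.1) adds minimum and maximum for continuous data, if that general rule applies to the laboratory tables. This stands. A reader might infer that renal, pancreatic or electrolyte abnormalities would appear in no categorical summary, or could be found only by reading listings. The documents do not support either inference.

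These routes still do not replace the endpoint. Adverse event tables depend on an investigator recording the finding, and they serve the first safety endpoint. The laboratory events of special interest cover transaminases (with bilirubin or INR), blood counts and CPK, so no such rule forces capture of the other analytes. Minimum and maximum show one extreme subject each, not a count.

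A second reply is that nothing was dropped. Section X calls the CTCAE work an addition, III.B keeps the full endpoint, and a low/normal/high classification is the usual input to ordinary shift tables. The SAP approval form lists data display shells separately from the text, and those shells are not available here. A reader might conclude that the sponsor removed the all-parameter tables. That cannot be shown, because silence fits either reading. It remains true that the SAP text, which takes precedence on methods, does not specify them.

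Third, the ten parameters are a sensible choice for CTCAE grading, since they include the laboratory events of special interest. That supports keeping those tables. It does not explain an endpoint that says all.

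**Conclusion.** The inconsistency is real. The endpoint covers shifts in all safety laboratory parameters; SAP IX.B specifies them for ten, in one direction, to the worst grade rather than by visit, and Section X does not declare the difference. For 17 of 22 chemistry analytes, the remaining hematology parameters and all three urinalysis items, the SAP text specifies no laboratory shift or abnormality-incidence table. The chemistry count comes straight from the SAP list; the overall 71% to 74% rests on the assumed size of the differential. The creatinine example uses assumed values and illustrates the mechanism only; it does not measure a loss in this trial.

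Severity is minor to moderate. The gap affects how completely the laboratory data are reported by arm. It does not affect efficacy inference, trial conduct or the data collected, and other routes give partial visibility.

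**What to change.** In SAP IX.B:
- Add low/normal/high shift tables, from baseline to the lowest and to the highest post-baseline class, by treatment group and period, for all hematology and serum chemistry parameters. This also gives the ten covered parameters their second direction.
- Add a normal/abnormal shift for urinalysis.
- Keep the CTCAE incidence and shift tables for the ten parameters.

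In SAP Section X, record that worst-value shifts replace the by-visit shifts of protocol 8.8.5, or produce the by-visit tables as well.

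The low/normal/high classes are already planned, so no new data are needed. The cost is SAP wording, standard programming and a longer table package. Narrowing the endpoint wording and declaring that in Section X would also remove the contradiction, but it would leave the analytes without a shift table uncounted.

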1. INTRODUCTION

1.1. Complement and Avacopan

The activation of the complement pathway generates biologically active fragments of complement proteins, e.g., C3a, C4a and C5a anaphylatoxins, and the C5b-9 membrane attack complex (MAC) or terminal complement complex (TCC), all of which mediate inflammatory responses by inducing leukocyte chemotaxis, activating macrophages, neutrophils, platelets, mast cells and endothelial cells and by increasing vascular permeability, cytolysis, and tissue injury.

C5a is one of the most potent pro-inflammatory mediators of the complement system, being at least 100 times more potent than C3a. This 12 to 14.5 kD polypeptide, along with a C5b fragment, is produced by enzymatic cleavage of a C5 precursor during activation of any of the 3 complement pathways. C5a induces expression of adhesion molecules and chemotactic migration of neutrophils, eosinophils, basophils, and monocytes. It also mediates inflammatory reactions by causing smooth muscle contraction, increasing vascular permeability, inducing basophil and mast cell degranulation, and inducing release of lysosomal proteases and oxidative free radicals. The anaphylactic and chemotactic effects of C5a are mediated through its interaction with the C5aR, a G protein-coupled receptor expressed on human neutrophils, monocytes, basophils, eosinophils, renal glomerular tissues, and lung smooth muscle and endothelial cells.

Avacopan (formerly CCX168) is an orally administered, small molecule, selective inhibitor of the complement 5a receptor (C5aR).

As measured in vitro, avacopan functionally inhibits C5a-mediated chemotaxis, displaces [¹²⁵I]-C5a from human C5aR, and inhibits C5a-mediated increase in cytoplasmic calcium levels with a potency (IC₅₀) of 0.2 to 0.9 nM in buffer (Bekker et al, 2016).

Avacopan was also evaluated for its ability to inhibit the C5a-mediated chemotaxis of neutrophils in freshly isolated human whole blood. Avacopan produced 50% inhibition (IC₅₀) of C5a-mediated neutrophil migration in this assay at a concentration of 1.7 nM; 90% inhibition (A₁₀ value) occurred at an avacopan concentration of 15.4 nM. Avacopan also inhibits C5aR in cynomolgus monkeys and hamsters with potencies similar to that observed with human whole blood. However, avacopan possesses moderate potency for rabbit C5aR (IC₅₀ ~ 1.4 μM) and lacks affinity for mouse, rat, or dog C5aR (IC₅₀ >10 μM).

The efficacy of avacopan was assessed using genetically-modified mice where the mouse C5aR coding region was substituted for the human C5aR coding region. In these studies, intravenous injection of mouse anti-myeloperoxidase (anti-MPO) IgG into the human C5aR knock-in mice caused glomerulonephritis in a manner mimicking anti-neutrophil cytoplasmic autoantibody (ANCA) disease in humans. At daily oral doses of 30 mg/kg avacopan, a marked inhibition of anti-MPO induced glomerulonephritis was documented histologically, as assessed by the number of necrotic and crescent-containing glomeruli. These results were consistent with reduced protein, leukocytes, and red blood cells in the urine, and reduced serum blood urea nitrogen and creatinine in mice receiving avacopan (Xiao et al, 2014).

1.2. Previous Clinical Studies

Five Phase 1 studies and four Phase 2 studies with avacopan have previously been completed. Avacopan was generally well tolerated in these studies. A Phase 3 study in subjects with AAV previously completed enrollment but follow up is ongoing and the study remains blinded. Another Phase 2 study in subjects with C3 glomerulopathy is currently enrolling and is also blinded.

Results from a mass balance study (CL004_168) showed that avacopan was mostly metabolized in the liver; in vitro metabolism studies showed that avacopan was primarily metabolized through cytochrome P450 3A4 (CYP3A4).

Avacopan did not show evidence of a detrimental effect on QT/QTc based on results from an intensive ECG study (CL007_168).

Co-administration of the strong CYP3A4 enzyme inducer rifampicin in study CL008_168 resulted in an approximately 93% reduction of systemic exposure of avacopan, which may result in a loss of efficacy of avacopan. Therefore, the use of strong CYP3A4 enzyme inducers with avacopan is an exclusion criterion for this study. Co-administration of the strong CYP3A4 enzyme inhibitor itraconazole resulted in a 119% increase of systemic exposure of avacopan. Concomitant use of avacopan with strong CYP3A4 enzyme inhibitors should be used with caution.

Two Phase 2 clinical trials in 109 subjects with ANCA-associated vasculitis (AAV) were conducted. The first study in 67 subjects (CL002_168) included three dose groups: 30 mg avacopan twice daily plus low dose prednisone (20 mg/day), 30 mg avacopan twice daily plus no prednisone, and placebo plus full dose prednisone (60 mg/day). All subjects received either IV cyclophosphamide or rituximab as standard of care treatment. Avacopan, alone or with low dose prednisone, was associated with a rapid onset of action based on improvements in a global disease activity index (the Birmingham Vasculitis Activity Score, BVAS), and improvements in renal parameters such as albuminuria, and health-related quality of life measurements over a 12-week treatment period (Jayne et al, 2017). The steady state mean avacopan plasma concentration was approximately 204 ng/mL in these subjects, corresponding to >95% projected inhibition of the C5aR in the circulation. Avacopan also showed a favorable safety profile in this study.

The second study in 42 subjects (CL003_168) included three dose groups: 10 mg avacopan twice daily plus full dose prednisone (60 mg), 30 mg avacopan twice daily plus full dose prednisone, and placebo plus full dose prednisone. All subjects received either IV cyclophosphamide or rituximab as standard of care treatment. Avacopan appeared to be safe when added on top of full dose prednisone plus cyclophosphamide or rituximab, and the efficacy data support 30 mg avacopan twice daily as the therapeutic dose in AAV. Refer to the [Investigator's Brochure](#) for more details.

An open-label Phase 2 clinical trial in 7 subjects with IgA nephropathy (IgAN) has been conducted (CL005_168). Results showed that avacopan therapy was associated with improvement in proteinuria over a 12-week treatment period; 3 of 7 subjects showed approximately 50% decrease in either urinary protein:creatinine ratio (UPCR) or albumin:creatinine ratio (UACR). An open-label Phase 2 clinical trial in 6 subjects with atypical hemolytic uremic syndrome (aHUS) was conducted (CL006_168). Results showed that serum

collected from subjects dosed with avacopan caused a mean percent reduction of 82% in thrombus size compared to baseline in an ex vivo assay.

A Phase 2 clinical trial with a target enrollment of approximately 88 subjects with C3 glomerulopathy is ongoing (CL011_168). The study remains blinded.

A Phase 3 clinical trial with a target enrollment of approximately 300 subjects with AAV previously completed enrollment and follow up is ongoing (ADVOCATE, CL010_168). In this study in subjects with AAV, avacopan (or placebo) is compared with standard of care glucocorticoids as added medications to background therapy of either rituximab or cyclophosphamide followed by azathioprine. The study remains blinded.

The Reference Safety Information section of the [Investigator's Brochure](#) has been updated to include the potential risk of urticaria, angioedema, and of hepatotoxicity, and to state that general gastrointestinal adverse events (e.g., nausea, diarrhea) observed in Phase 2 AAV studies have been observed in the ongoing Phase 3 CL010_168 study at approximately the same frequency and severity. Further, as a result of the DMC review of safety data from all completed and ongoing studies of avacopan, the frequency of monitoring of hematology has been increased to monthly and rules for pausing administration of blinded study drug have been modified.

A benefit and risk assessment of avacopan is presented in [Section 11](#); detailed information about non-clinical and clinical trials with avacopan is presented in the Investigator's Brochure. Results from nonclinical and clinical studies conducted to date showed a positive risk-benefit profile of avacopan in treatment of subjects with HS ([Section 11](#)).

